10.2.2 Descriptive Statistics

Within each randomized treatment group appropriate descriptive statistics including means and standard deviations for quantitative variables and frequency and percentages for categorical variables will be calculated. Wilcoxon Rank Sum test and Fisher's exact test will be used to compare the two intervention groups with respect to the following baseline variables:

- Demographics (age, sex, race, ethnicity)
- Initial pain intensity and duration
- Pain medication use
- Pain Catastrophizing Scale
- Initial diagnosis (symptomatic irreversible pulpitis with/without symptomatic apical periodontitis and pulp necrosis with symptomatic apical periodontitis)
- Initial clinical testing of cold response (positive/negative)
- Initial clinical testing of percussion hypersensitivity (painful/not painful)

Any variable deemed significant will be controlled for in the primary, secondary and exploratory analyses. All analyses will be done with significance level of 5% (2-sided) unless specified otherwise.

CONFIDENTIAL

10.2.3 Primary Analysis

For the primary objective we will compare the oral quality of life OHIP-14 score change from preoperative baseline to day 1 postoperatively and the change from preoperative baseline to day 5 postoperatively between the 2 arms using a two-sample t-test (or a Wilcoxon Rank Sum test if data are not normally distributed) for each comparison individually at 2.5% significance level (2-sided) adjusted for the two comparisons using a Bonferroni correction. If at least one of the changes, either from baseline to day 1 postoperatively or from baseline to day 5 postoperatively, is significantly different between the 2 groups, the null hypothesis will be rejected.

For each of the 7 sub-domains of OHIP-14 we will calculate the mean change from preoperative baseline to day 1 and to day 5 in both arms.

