Statistical Analysis	
For the primary objective we will compare the oral quality of life OHIP-14 score change from preoperative baseline to day 1 postoperatively and the change from preoperative baseline to day 5 postoperatively between the 2 arms using a Wilcoxon Rank Sum test for each comparison individually at 2.5% significance level (2-sided) adjusted for the two comparisons using a Bonferroni correction. If at least one of the changes, either from baseline to day 1 postoperatively or from baseline to day 5 postoperatively, is significantly different between the 2 groups, the null hypothesis will be rejected.
 
For each of the 7 sub-domains of OHIP-14 we will calculate the mean change from preoperative baseline to day 1 and to day 5 in both arms.
 
For the secondary objective we will compare the efficacy of bupivacaine with that of lidocaine over the postoperative 5 days using mixed models for longitudinal data. The efficacy will be compared in terms of the following measures:
 
1. postoperative pain resolution2. pain medication use3. numbness (duration of LA) after receiving endodontic treatment 
The success of LLA will be determined by the cold test results (+/-) and the number of supplemental injections. The onset of LLA will be determined by the duration until adequate lip numbness and the duration until negative cold response after IANB.
 
For the exploratory objective we will compare the success and onset of LA in the two study arms. For comparison of success of LLA between the 2 arms we will use Fisher's exact test. For comparison of onset of LLA between the 2 arms we will use a Wilcoxon Rank Sum test.
 
Ad Hoc Stopping Rule
 
After 40 patients are accrued (approximately 20 subjects in each arm) an ad-hoc analysis will be performed to assess and compare the success of LA in both groups. If the proportion of subjects who are excluded intraoperatively in the study arm is twice as large as that of the control arm, the study will be terminated. The reasons for being excluded intraoperatively are if adequate lip numbness is not obtained with 2 inferior alveolar nerve block anesthesia and/or adequate pulpal anesthesia is not obtained after 2 times of supplemental anesthesia. Although, this is not a safety issue, we do not want to create more risks of intraoperative pain than routine endodontic practice. This analysis will be done by the study statistician. The investigators will remain blinded to the subjects' treatment arm.

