7.2.2 Baseline

Baseline (Day 0/Day 1)

- Verify the diagnosis and the treatment plan for the tooth.
- Verify eligibility by reviewing inclusion/exclusion criteria
- Preoperative data collection: results of routine clinical and radiographic examination, endodontic diagnosis,
- Baseline OHIP14 questionnaire

Treatment

- Administer the study intervention and dental treatment
- Collect intraoperative pain with a questionnaire to the subject after the completion of the treatment.

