10.1 Sample Size Determination

Based on a previous study, the mean change of overall OHIP-14 scores from baseline at 1 month follow up is 6 with a standard deviation of 13.3 (27). Assuming the mean change from preoperative baseline at day 1 and day 5 postoperatively in the lidocaine group is 6 and the standard deviation is 13.3 and assuming the standard deviation of the change from baseline at day 1 and day 5 postoperatively is the same in the bupivacaine group, then with 40 subjects in each of the 2 groups there is 80% power to detect a difference in the change from preoperative baseline of +/-9.3 between the 2 groups. Assuming significance level of 2.5% using a 2-sided 2-sample t-test (assuming the data are Normally distributed). The testing is done at 2.5% because the null hypothesis will be rejected if at least one of the changes, either from baseline to day 1 postoperatively or from baseline to day 5 postoperatively, is significantly different between the 2 groups.

Considering the dropout rate after randomization will be 20%, the total number of subjects need to be enrolled is 100. The dropped-out subjects are those who are needed to be excluded because of intraoperative exclusion criteria, and who are not compliant to complete postoperative questionnaires. NYU Dentistry, endodontic clinic is a busy clinic. We will most of the time recruit subjects from the endodontic emergency care where on a daily basis, on average 5 patients are being treated. However, we are unsure of how many cases will be screened in order to reach this approximate sample size but we will update the protocol as this information is obtained.

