10.2 Statistical Analysis

10.2.1 Analysis Dataset

The analysis dataset for study and control group will include subjects who receive IANB either with the study agent Bupivacaine or the control agent Lidocaine for the pulpectomy/endodontic debridement of symptomatic mandibular molar teeth diagnosed with either symptomatic irreversible pulpitis or pulp necrosis and periapical diagnosis of normal periapical tissues, asymptomatic or symptomatic apical periodontitis. The dataset will consist of preoperative data (demographics, preoperative pain assessment, PCS, LOT-R), initial clinical examination (cold test, percussion hypersensitivity), diagnosis, intraoperative data, initial and follow up OHIP-14 scores and postoperative pain, medication use and numbness. All analyses will be intent-to-treat dataset that includes all randomized patients and will use the analysis dataset.

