10.2.4 Secondary Analysis

1. For the secondary objective we will compare the efficacy of bupivacaine with that of lidocaine over the postoperative 5 days using mixed models for longitudinal data. The efficacy will be compared in terms of the following measures: postoperative pain resolution,
2. pain medication use,
3. numbness (duration of LA) after receiving endodontic treatment

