10.2.5 Exploratory Analysis

The success of LLA will be determined by the cold test results (+/-) and the number of supplemental injections. The onset of LLA will be determined by the duration until adequate lip numbness and the duration until negative cold response after IANB.

For the exploratory objective we will compare the success and onset of LA in the two study arms. For comparison of success of LLA between the 2 arms we will use Fisher's exact test. For comparison of onset of LLA between the 2 arms we will use a Wilcoxon Rank Sum test.

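### The primary OHIP-14 analysis is not fixed in advance: two sections name different tests, covariates enter only after a significant baseline test with no adjusted model named, and baseline OHIP-14 is used only by subtraction.

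*Combined protocol and SAP*

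**What the plan says.** **Test.** Section 10.2.3 compares the change in OHIP-14 to day 1 and to day 5 "using a two-sample t-test (or a Wilcoxon Rank Sum test if data are not normally distributed) for each comparison individually at 2.5% significance level". The statistical paragraph of the Protocol Summary describes the same comparison "using a Wilcoxon Rank Sum test for each comparison individually at 2.5% significance level (2-sided") and mentions no t-test. The section on sample size determination relies on a t-test: "Assuming significance level of 2.5% using a 2-sided 2-sample t-test (assuming the data are Normally distributed"). The 2.5% level per day and the rule that either day suffices agree in all three places.

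**Covariates.** Section 10.2.2 tests a list of baseline variables between arms with Wilcoxon and Fisher tests, at 5% by default, and then states: "Any variable deemed significant will be controlled for in the primary, secondary and exploratory analyses". It names no adjusted model.

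**Baseline OHIP-14.** Section 7.2.2 lists the "Baseline OHIP14 questionnaire", and section 10.2.1 places "initial and follow up OHIP-14 scores and postoperative pain, medication use and numbness" in the analysis dataset. Baseline OHIP-14 is not on the section 10.2.2 list and is nowhere named as a covariate.

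**Other analyses under the same covariate rule.** In section 10.2.4, "we will compare the efficacy of bupivacaine with that of lidocaine over the postoperative 5 days using mixed models for longitudinal data". In section 10.2.5, "For comparison of onset of LLA between the 2 arms we will use a Wilcoxon Rank Sum test", and anesthetic success is compared by Fisher's exact test.

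**The concern.** Three things that should be settled before the data are seen are left open.

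1. Two current sections disagree on the primary test. The one that allows a choice does not say how normality is judged, at what threshold, or when.
2. Under 1:1 randomisation, a significant baseline difference is a chance event. A rule triggered by it picks covariates for imbalance, not for prognostic value. Section 2.1 describes preoperative pain as a major predictor of postoperative pain, yet it would be adjusted for only if the arms happened to differ on it.
3. Neither primary test, as written, comes with a way to adjust. Once a baseline test is significant, the deciding p-value must come from a model that the plan does not specify. The same gap exists for the Fisher and Wilcoxon tests in section 10.2.5.

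Separately, a baseline value that is already collected, and that could sharpen the primary comparison at no data cost, is used only by subtraction.

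**Working it through.** **1. The plan's own figure.** Inputs from the sample-size section: change SD 13.3 in both arms, 40 per arm, difference 9.3, two-sided 2.5%.
- Standard error = 13.3 × √(2/40) = 2.974.
- Noncentrality = 9.3 / 2.974 = 3.127, with 78 df and critical t 2.285.
- Power = 79.8%, and the difference detectable at 80% power is 9.32.
- Enrolment = 80 / 0.8 = 100.

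The stated 80% power, 9.3 and 100 all reproduce.

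**2. The choice of test.**
- For normal data the Wilcoxon test has relative efficiency 3/π. Using SD 13.3/√(3/π) in the same formula gives 77.8% power at 9.3, so the two named tests are not the same plan.
- If the smaller of the two p-values were taken, simulation at 40 per arm put per-comparison type I error at about 3.0 to 3.5%, depending on the shape of the data, against 2.5%.
- With a fixed rule (Shapiro-Wilk at 5%), simulated error was 2.3 to 2.7%.

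**3. The covariate rule.** Split into single items, the section 10.2.2 list gives 11 variables:
- four for Wilcoxon (age, pain intensity, pain duration, catastrophizing);
- five binary for Fisher (sex, ethnicity, medication use, cold response, percussion);
- diagnosis (three categories) and race (taken as four).

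Actual test sizes at 40 per arm: Wilcoxon 0.048, or 0.05 for the NRS; Fisher 2×2 from 0.017 to 0.033 for assumed prevalence 0.1 to 0.5; diagnosis 0.047; race taken as 0.05. If the tests are independent, the chance of at least one significant result is

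1 − 0.952³ × 0.95 × 0.953 × 0.95 × (1 − f)⁵

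which is 31.9% at f = 0.017 and 37.3% at f = 0.033. The ceiling with exact 5% tests is 1 − 0.95¹¹ = 43.1%. With an assumed shared correlation of 0.3 to 0.5 among most of the variables, a simplified simulation gave about 26 to 31%.

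The rule was also simulated in full (30,000 runs; race and diagnosis dichotomised; three prognostic covariates with assumed coefficients):

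| Coefficient per SD | Type I error | Power under rule | Power unadjusted | Difference (points) |
|---|---|---|---|---|
| 0 | 2.53% | 78.2% | 79.6% | −1.4 |
| 0.3 | 2.05% | 80.0% | 80.1% | −0.1 |
| 0.45 | 1.65% | 81.4% | 80.3% | +1.1 |

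**4. Baseline OHIP-14 as a covariate.** The documents give neither the baseline/follow-up correlation ρ nor the ratio k of follow-up SD to baseline SD, so both are assumed. With k = 1 and change SD held at 13.3, the residual SD is 13.3 × √((1+ρ)/2). The calculation uses 77 df and multiplies the variance by 1 + 1/76 for estimating the slope.

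| ρ | Residual SD | Power at 9.3 | Detectable difference |
|---|---|---|---|
| 0.3 | 10.72 | 93.9% | 7.56 |
| 0.5 | 11.52 | 90.1% | 8.13 |
| 0.7 | 12.26 | 85.8% | 8.65 |

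Over k from 0.6 to 1.5 and the same correlations, simulated power ran from 99.9% down to 79.3%. When the slope ρ × k is 1, the residual SD is again 13.3 and power is 79.2%, a loss of about 0.6 points against 79.8%. Simulated ANCOVA type I error was 2.3 to 2.6%, including with skewed data.

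**The case against.** The strongest reply has four parts.

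- *The change-score t-test is valid and already uses baseline OHIP-14.* This stands. Leaving the baseline out as a covariate is a missed improvement, not an error, and the size of the gain cannot be established from the documents.
- *The covariate rule is mechanical and does little.* It uses baseline data only, a listed set and a 5% level, so it is not discretion over outcomes. It moves power by about −1.4 to +1.1 points. This stands too. What remains is that the rule leads to a model nobody has named. A stratified rank test could handle categorical variables, for example, but the plan does not choose it.
- *The test conflict could be repaired by aligning the Summary with section 10.2.3 and stating a normality rule.* True, and that would remove most of the error concern. It would still leave the primary method to depend on the outcome data.
- *Adjusting for observed imbalance is common.* It may be, but the adjusted model must still be stated.

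A reader might infer that the plan biases the comparison or inflates type I error as written. The documents do not support that. A single fixed change-score test holds its level, and the simulated covariate rule stayed at 1.7 to 2.5%. The 3.0 to 3.5% arises only if someone takes the smaller p-value, which the plan does not say will be done. Nor does the point undermine the sample size.

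**Conclusion.** The concern holds as a specification gap in the primary analysis, together with an inexpensive improvement. From the text alone, the primary test differs between two sections, the normality switch has no criterion, and the baseline-test rule names no adjusted model. The size of the problem is modest. An unnamed model would be needed in about 32 to 37% of trials if the 11 tests are independent, with assumed category frequencies, and in fewer if they correlate. The error rate from the open test choice is bounded at about 3.0 to 3.5% per comparison. The precision gain of about 94, 90 or 86% power against 79.8% depends on assumed correlations of 0.3, 0.5 or 0.7 and equal SDs. It shrinks to nothing, or to a loss of about 0.6 points, as the baseline slope approaches 1. The change should be made, but the trial is not invalid without it.

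**What to change.** **Protocol Summary and section 10.2.3.** State one primary analysis in both: an ANCOVA of OHIP-14 on arm and baseline OHIP-14, at day 1 and at day 5, each at 2.5% two-sided with ordinary model-based standard errors. The day score and the change score give the same arm effect. Remove the normality switch, and keep the Wilcoxon test on change as a named sensitivity analysis.

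**Section 10.2.2.** Delete the between-arm significance tests and the sentence that makes adjustment depend on them. Keep the descriptive table. Prespecify any covariates for the other analyses on prognostic grounds. Section 2.1 supports preoperative NRS pain for the pain model. The documents give no comparable basis for the medication, numbness, success or onset analyses, so the sponsor should either justify covariates there or state that there are none.

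**Sample size determination.** Keep the present sizing, and add that it is based on the unadjusted t-test and is generally conservative for the ANCOVA.

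**Cost.** One amendment, which section 13.2 requires the IRB to approve before it takes effect, made before unblinded OHIP-14 data are seen. It needs no new data and no extra participants, and it loses at most about 0.6 points of power if the baseline slope is near 1.

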3.1 Primary Objective

Assess whether pulpectomy/endodontic debridement with 0.5% bupivacaine with 1:200,000 epinephrine (as a LLA) differs with respect to changes from preoperative baseline to postoperative day 1 or day 5 in oral health related quality of life (as measured by OHIP-14 questionnaire), than treatment with 2% Lidocaine with 1:100,000 epinephrine.

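### Bonferroni at 2.5% per day is valid, but a pre-specified Holm step would add power for the day-specific conclusions at the same 5% family-wise error rate

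*Combined protocol and SAP*

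**What the plan says.** Section 10.2.3 (Primary Analysis) compares the two arms on OHIP-14 change from baseline to day 1 and from baseline to day 5, "for each comparison individually at 2.5% significance level (2-sided"), "adjusted for the two comparisons using a Bonferroni correction". The tests are made "using a two-sample t-test (or a Wilcoxon Rank Sum test if data are not normally distributed"). If at least one of the two changes "is significantly different between the 2 groups, the null hypothesis will be rejected". The Statistical Analysis entry of the Protocol Summary has the same 2.5% level and the same at-least-one rule, but names only the Wilcoxon test.

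The primary objective (section 3.1) asks whether bupivacaine "differs with respect to changes from preoperative baseline to postoperative day 1 or day 5 in oral health related quality of life". Section 10.1 (Sample Size Determination) uses the same level: "Assuming significance level of 2.5% using a 2-sided 2-sample t-test (assuming the data are Normally distributed"). It gives 80% power for a difference of 9.3 with 40 evaluable subjects per arm. No step-down procedure is mentioned, and no success criterion or power is given for showing an effect on both days.

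**The concern.** The plan tests each day at 2.5% whatever the other day shows. Once one day has been rejected at 2.5%, the remaining hypothesis can be tested at 5% without the family-wise error exceeding 5%. The fixed 2.5% for the second day is therefore stricter than family-wise control requires.

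The at-least-one-day conclusion does not depend on this. What is at stake is the statement about each day. The plan tests the days individually, and a global rejection does not say whether day 1, day 5 or both differ. Readers of the result will want to know, and that is where the extra power applies.

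**Working it through.** **Inputs.** From section 10.1 (Sample Size Determination): 40 evaluable per arm, SD of change 13.3 in both arms and on both days, difference 9.3, two-sided 2.5%, 20% dropout. From section 10.2.3: two tests at 2.5% each, reject if at least one is significant, so the family-wise level is 2 × 2.5% = 5%. The correlation between the day 1 and day 5 changes is not in the documents. It is an assumption, with 0.3 to 0.7 as the working range and 0 and 0.9 as extremes.

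**Step 1: the plan's own figure.** The standard error of the difference is 13.3 × √(2/40) = 2.974, so the standardised difference is 9.3/2.974 = 3.127. The normal approximation gives Φ(3.127 − 2.241) = 81.2%. The noncentral t with 78 degrees of freedom gives 79.8%, with a detectable difference of 9.32 at 80% power. Enrolment is 80/(1 − 0.20) = 100. The stated 80%, 9.3 and 100 all reproduce.

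**Step 2: error control.** Holm compares the smaller p-value with 2.5% and, only if that is significant, the larger with 5%.

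- Both nulls true: an error needs the smaller p-value at or below 2.5%. The probability is at most 2.5% + 2.5% = 5%.
- One null true: an error needs that day's p-value to be at or below 5%. The probability is at most 5%.

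Neither bound uses the correlation. The first step is the plan's own test, so the at-least-one-day decision is the same in every dataset.

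**Step 3: power when the true difference is 9.3 on both days.** Two correlated two-sample t-tests, 400,000 simulated trials per row (gains taken before rounding):

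| Correlation (assumed) | At least one day, either method | Both days, Bonferroni | Both days, Holm | Gain (points) | Given single day, Bonferroni | Given single day, Holm |
|---|---|---|---|---|---|---|
| 0 | 95.9% | 63.8% | 75.3% | 11.5 | 79.8% | 85.6% |
| 0.3 | 93.4% | 66.4% | 76.8% | 10.3 | 79.9% | 85.1% |
| 0.5 | 91.4% | 68.4% | 78.0% | 9.6 | 79.9% | 84.7% |
| 0.7 | 88.7% | 71.0% | 79.5% | 8.4 | 79.9% | 84.1% |
| 0.9 | 84.9% | 74.7% | 81.5% | 6.7 | 79.8% | 83.2% |

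The columns agree with each other. With equal effects the single-day gain is half the both-days gain, because either day is equally likely to be the one rescued at 5%. At correlation 0.5, 9.6/2 = 4.8, and 84.7 − 79.9 = 4.8.

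**Step 4: unequal effects.** With 9.3 on day 1 and half of that, 4.65, on day 5 (an assumption), both-days power at correlation 0.5 goes from 22.9% to 32.4%.

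**Step 5: what Holm costs.**

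- Both nulls true: rejection of at least one falls from 4.9% to 3.7% as the correlation rises from 0 to 0.9, the same under both methods.
- 9.3 on day 1 and no effect on day 5: the false day 5 claim rises from 2.5% to between about 4.1% and 4.4% for correlations 0.7 to 0.3.
- A very large effect on day 1 (30) and none on day 5: the false day 5 claim rises from 2.5% to 5.0%, the limit.

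**The case against.** The strongest case on the other side is that nothing here is wrong. Bonferroni is valid, is stated alike in the summary and in section 10.2.3, and matches the level used for the sample size. The objective is day 1 or day 5, so the formal question gains nothing from Holm. All of this stands, and it makes the point an optional improvement.

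Three stronger readings might be inferred, and the documents do not support them.

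- *The plan is underpowered for its second statement.* Each day taken alone has about 80% power for 9.3. The 68% is for showing both days together, which the plan never set as a goal.
- *Holm costs nothing.* Step 5 shows that it uses error that Bonferroni leaves unspent, and this falls on the day-specific claim. Bonferroni also pairs each test with a 97.5% confidence interval. Under Holm, a second day with a p-value between 2.5% and 5% is declared different while its 97.5% interval still includes zero.
- *Day 1 measures the anaesthetic period and day 5 the lasting effect.* The Protocol Summary puts anaesthesia at up to 7 hours for bupivacaine and up to 4 for lidocaine, and section 2.1 mentions 7 to 12 hours. Numbness is surveyed separately from 6 hours on, and no recall period is stated for OHIP-14. Sections 2.1 and 2.3 suggest that benefit may outlast the anaesthesia, which could apply to either day.

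**Conclusion.** The point holds as a low-cost improvement, not as the correction of an error. Holm rejects everything that Bonferroni rejects and sometimes one day more, with family-wise error at or below 5% under any dependence. At the design values, both-days power rises by about 8 to 10 points and single-day power by about 4 to 5 points (from 80% to roughly 84% to 85%). The primary decision, its power and the 40 evaluable per arm do not change.

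The error bound needs no assumption about correlation. The size of the gain does: it rests on the assumed range of 0.3 to 0.7, normal data, SD 13.3 and a true difference of 9.3 on both days. The advantage concerns rejections only. For simple simultaneous intervals, Bonferroni remains the more direct choice.

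**What to change.** In section 10.2.3 and in the Statistical Analysis entry of the Protocol Summary, replace the Bonferroni clause with:

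> The smaller of the two p-values is compared with 2.5%; if significant, the larger is compared with 5% (Holm).

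Keep the rule that the null hypothesis is rejected if at least one day is significant, and leave section 10.1 (Sample Size Determination) as it is. Holm works on the p-values, so it applies to the t-test and the Wilcoxon test alike. The 97.5% intervals can still be reported for each day, with a note that the second test may reject where its interval includes zero.

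The change must be made before unblinding. Subjects are told their product at the second visit (section 13.3.1), so it is best dated before anyone sees OHIP-14 results by arm. The cost is one sentence in two places and the higher false-positive rate on the second day, still within the 5% limit.
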